 4. ESR
- Proportion of subjects with clinically important reduction in SLE activity at each time point, based on CRV changes compared to baseline
- Proportion of subjects with flare of SLE activity at each time point, based on CRV changes compared to baseline

Data of subjects who enter Part B before week 8 and/or Part C before week 24 will be considered on a last-observation (LOC) carried forward basis for endpoints of Part A and B, respectively.

C. INCLUSION/EXCLUSION CRITERIA

INCLUSION CRITERIA

1. Male or female age 18 to 45 years and >40 kg body weight.
2. Fulfills at least 4 out of the 11 Classification Criteria for SLE by the time of screening.
3. Written informed consent, given before any trial-related procedure. Subjects or their legal representative must have read and understood the informed consent form, must fully understand the requirements of the trial, and must be willing to comply with all trial visits and assessments.
4. CLASI activity score of 8 or higher at screening and baseline despite standard therapy.
5. Stable dose of prednisone of ≤ 20 mg/day within 2 weeks of enrollment.
6. Female subjects of childbearing potential must use a highly effective method of contraception to prevent pregnancy (abstinence is considered highly effective) and must agree to continue

to practice adequate contraception for the duration of their participation in the trial and for 28 days following the last dose of TOFA.

7. Female subjects of childbearing potential must have a negative serum pregnancy test at screening and a negative urine pregnancy test at Trial Day 1 before dosing.
8. For subjects receiving leflunomide treatment, total daily dose does not exceed 20 mg.
9. A negative QuantiFERON-TB Gold In-Tube test performed within the 3 months prior to screening. A negative PPD test can be substituted for the QuantiFERON-TB.
10. Patients either have protective varicella titers or evidence of having been vaccinated against varicella.

EXCLUSION CRITERIA

Subjects are not eligible for this trial if they fulfill any of the following exclusion criteria:

1. Mild SLE -CL defined as a CLASI activity score of 7 or lower at screening and baseline
2. Increase in CS dosing within 2 weeks prior to Trial Day 1, or expected to require an increase in CS dosing during the first 4 weeks of the study.
3. Use of i.v. corticosteroids within 4 weeks prior to Trial Day 1.
4. Increase in dosing of methotrexate, leflunomide, within 4 weeks before Trial Day 1 or expected to require an increase during the first 8-weeks of the study
5. Increase in dosing of hydroxychloroquine, or chloroquine within 4 weeks before Trial Day 1 or expected to require an increase during the first 8-weeks of the study
6. Rituximab within 1 year of Trial Day 1.
7. Increase in dosing of any medication or herbal treatment considered to have immunosuppressive properties within 4 weeks before Trial Day 1.
8. Prior treatment with or known intolerance of TOFA.
9. Use of cyclophosphamide (i.v. or oral), cyclosporine, or tacrolimus within 12 weeks prior to Trial Day 1.
10. Treatment with other investigational agents within the last 6 months or 5 half-lives, or as per washout requirement from the previous protocol, whichever is longer.
11. Estimated glomerular filtration rate (GFR) less than or equal to 60 mL/min per 1.73 m²
12. Known positive human immunodeficiency virus (HIV), hepatitis C virus (HCV), or hepatitis B surface antigen (HBsAg) serology.
13. Any condition, including findings in the laboratory tests, medical history, or other screening assessments, that, in the opinion of the Investigator, constitutes an inappropriate risk or a contraindication for participation in the trial or that could interfere with the trial's objectives, conduct, or evaluation.

14. Active central nervous system SLE deemed to be severe or progressive and/or associated with significant cognitive impairment leading to inability to provide informed consent and/or comply with the protocol.
15. Significant renal disease due to a reason(s) other than LN (e.g. diabetes mellitus, renovascular disease, or antiphospholipid syndrome).
16. Severely active Lupus Nephritis defined as a renal BILAG A score
17. History of dialysis within 3 months prior to Trial Day 1 or expected use during the trial duration.
18. History of or planned renal or other organ transplantation.
19. Known active clinically significant viral, bacterial or fungal infection, or any major episode of infection requiring hospitalization or treatment with parenteral anti-infectives within 8 weeks of screening, or completion of oral anti-infectives within 2 weeks before trial Day 1.
20. Breastfeeding or currently pregnant.
21. Legal incapacity or limited legal capacity to provide informed consent or assent.
22. Blood dyscrasias, including:
 - Hgb <10 g/dL or Hct <33%.
 - WBC <3.0 x 10⁹/L.
 - Neutrophil count <1.2 x 10⁹/L
 - Platelet count <100x 10⁹/L.
 - Lymphocyte count of <0.5 x 10⁹/L.
23. AST or ALT > 1.5 times the upper limit of normal or any other clinically significant laboratory abnormality.
24. History of any other rheumatic autoimmune disease.
25. Infections:
 - Latent or active TB or any history of previous TB.
 - Chronic infections.
 - Any infection requiring hospitalization, parenteral antimicrobial therapy or judged to be opportunistic by the investigator within the 6 months prior to the first dose of study drug.
 - Any treated infections within 2 weeks.
 - History of recurrent (more than one episode) herpes zoster or disseminated (a single episode) herpes zoster or disseminated (a single episode) herpes simplex.
 - History or current symptoms suggestive of any lymphoproliferative disorder, including Cytomegaly Virus (CMV) or Epstein Barr Virus (EBV) related lymphoproliferative disorder, history of lymphoma, leukemia, or signs and symptoms suggestive of current lymphatic disease.
26. Patients taking potent and moderate cytochrome P450 3A4 (CYP3A4) inhibitors.

27. Patients taking potent and moderate CYP3A4 inducers.
28. Patients who have been vaccinated with live or attenuated vaccines within the 6 weeks prior to the first dose of study medication. All study participants should be up-to-date with respect to standard of care vaccinations (as defined by their country health ministry) as permitted by past immunosuppressive therapy for SLE.
29. Patients with a malignancy or with a history of malignancy with the exception of adequately treated or excised non-metastatic basal cell or squamous cell cancer of the skin or cervical carcinoma in situ.
30. Subjects with a history or current diagnosis of diverticulitis.

D. SAMPLE SIZE

This is a 3-part study designed to evaluate the PK-PD of TOFA in subjects 18-45 years with at least moderately active SLE -CL. Safety and efficacy will be evaluated as secondary objectives. No formal sample size estimation was done but previous TOFA studies in other populations suggest that 20 subjects are sufficient to achieve the objectives of this study.

It is planned to enroll:

Cohorts 1: n=10, weight > 40 kg and age \geq 18 years up to and including age 45 years.

Cohort 2: n=10; weight > 40 kg and age \geq 18 years up to and including age 45 years. Enrollment of subjects into Cohort 2 will commence once enrollment of Cohort 1 are completed and at least 1 subject in Cohort 1 showed at least partial improvement of SLE-CL. i.e. a 20% reduction of the CLASI activity score, between baseline and week 4.

E. TRIAL MANAGEMENT

For this study, all subjects will be recruited and followed at CCHMC and Metrohealth Medical Center.

It is planned to enroll:

Cohorts 1: n=10, weight > 40 kg and age \geq 18 years and \leq 45 years.

Cohort 2: n=10; n=10, weight > 40kg and age \geq 18 years and \leq 45 years .

Enrollment of subjects into Cohort 2 will commence enrollment of Cohort 1 are completed and at least 1 subject in Cohort 1 showed at least partial improvement of SLE-CL. i.e. a 20% reduction of the CLASI activity score, between baseline and week 4.

The general approach to evaluation is to enroll a total of 20 subjects aged 18 to 45 years with a body weight of > 40 kg. Besides population PK-sampling, Cohort 1 will undergo intense PK-evaluations during the Intense PK Period of Part A. Enrollment of subjects into Cohort 2 will commence once enrollment of Cohort 1 are completed and at least 1 subject in Cohort 1 showed at least partial improvement of SLE-CL. i.e. a 20% reduction of the CLASI activity score, between baseline and week 4. Subjects move from Part A to Part B to Part C of the study, unless they are discontinued from the study (see rescue clause Section 6.5 in the clinical protocol).

It is anticipated that almost all subjects are on stable background therapy with an antimalarial (hydroxychloroquine, rarely chloroquine), up to 80% are treated with corticosteroids (CS), and about 50% of the subjects will also be treated with a non-biological DMARD (mostly methotrexate, azathioprine and mycophenolate mofetil) for prior multiorgan involvement with SLE.

Based on TOFA PK in the RA population (body weight ranging from 40 kg-140 kg), clearance (CL) of TOFA is not dependent on body weight in adult subjects. Thus, the dose of TOFA in adults with body weight (BW) ≥ 40 kg was set to 5 mg twice daily (BID), an approved dose of TOFA in adult RA patients in most countries.

This clinical trial is the only one planned to be conducted this year under the IND. The trial will take 4 years.

F. TARGET POPULATION DISTRIBUTION (WOMEN, MINORITIES, ETC)

Twenty adult subjects diagnosed with SLE will be enrolled in this study. All subjects regardless of race and socioeconomic class will be considered potential study subjects.

This study follows procedures for minimizing risks and ensuring the safety and confidentiality of human subjects, as established under both the Department of Health and Human Services and the Office for Human Research Protections (OHRP). The study will be conducted in accordance with the ethical principles of the Declaration of Helsinki and will be consistent with Good Clinical Practices (GCP) <http://www.fda.gov/cder/guidance/959fnl.pdf> and applicable regulatory requirements.

A common consent and assent form describing all aspects of the study will be used. Each participant and their legal guardian will be educated about their risks and potential benefits. We will take appropriate measures to ensure the confidentiality of the data and the well-being of participants.

G. INSTITUTIONAL REVIEW BOARD PROTOCOL REVIEW

The protocol, informed consent, and assent will be reviewed and approved by the IRB.

Recruitment & Consent Procedures

The recruitment procedures for the trial will include a thorough explanation of the study, time commitments, possible risks and benefits, and alternative treatments. The patient must sign an informed consent form that meets all current criteria of the FDA and local health regulations.

H. DATA SAFETY AND MONITORING PROCEDURES

All questionnaires and the results of the physical examination will be recorded on study forms. All forms will be assessed for completeness by the Clinical Research Coordinator. The Division of Rheumatology at Cincinnati Children's Hospital Medical Center will serve as study Coordinating Center.

ACTIONS TO ACHIEVE DATA SAFETY

All data will be entered into the Medidata Rave database on PCs in the Division of Rheumatology, CCHMC, stored and accessed in accordance with the HIPPA Standards [www.hhs.gov], HCFA's Internet Security Policy and other state and local requirements. The Medidata Rave database is maintained on servers by Medidata and back up is performed as outlined by medidata information security and privacy white paper. The Division of Biomedical Informatics at CCHMC distributes numerous computer packages for research purposes, including SAS [SAS Inc., Cary, North Carolina) and Microsoft software [see <http://info.chmcc.org>). Data monitoring of data collected at the CCHMC will be performed by the Division of Rheumatology research staff with assistance from the CCHMC *Office for Clinical and Translational Research* (OCTR).

MONITORING OF SITES

The PI will monitor the database of both CCHMC and Metrohealth Medical Center with assistance from CCHMC OCTR.

REPORTING OF ADVERSE EVENTS

Reporting of Adverse events will occur as part of the safety assessment of the study drug. We will use the National Cancer Institute (NCI) Common Toxicity Criteria, Version II for reporting.

All severe adverse events communicated to CC within one working day will be reported to the IRB within 2 working days. Based on the requirements for IND amendments outlined in the CFR §312.32, [name] will be responsible for IND safety reporting including reporting of life-threatening and serious adverse events, unexpected adverse drug experience and the writing of the annual IND safety report.

CRITERIA FOR STUDY DISCONTINUATION

A subject will be considered a treatment failure and discontinued from the study if he/she experiences one or more of the following:

- Serious adverse event that is possibly related to TOFA;
- Important worsening of renal disease defined as a persistent increase in proteinuria as measured by the protein: creatinine (PC) ratio to values > 2.0 after achieving complete response, or doubling of proteinuria with values PC ratio >3.0 after achieving a partial response;
- Need to increase current or initiation of new SLE background therapy due to non-renal SLE;

- Life-threatening SLE complications as judged by the investigator;
- Need for more than the allowable CS rescue therapy as determined by the treating physician.
- No response of SLE-CL by Week 8

INTERIM ANALYSIS & SAFETY REVIEWS

No interim analyses are planned. The PI will continuously monitor the study for safety. An internal review of the study will be completed by CCHMC OCTR as outlined in the monitoring plan.

I. DATA MANAGEMENT

GENERAL INSTRUCTIONS FOR COMPLETING FORMS.

All data recorded on forms must be verifiable in the source documents maintained according to FDA and Good Clinical Practice (GCP) guidelines.

Subjects must not be identified by name on any study document submitted with the forms (i.e. lab reports). Replace subject names with subject initials and ID number.

Source documentation will comply with the following:

- **HEADER:** Complete the header information on every page, including pages for which no study data are recorded. Record subject's first, middle, and last initials (use a hyphen if no middle name). All dates must be verifiable by source documentation. Estimates are not acceptable.
- **ABBREVIATIONS:** Use of abbreviations not specifically noted in the instructions for completing the forms can be problematic and should be held to a minimum.
- **EXTRANEOUS WRITING:** Comments written extraneously on forms cannot be captured for monitoring and data analysis; thus, write only in the spaces indicated.
- **CORRECTING ERRORS:** If an error has been made on the study forms, place a **single** line through the erroneous entry and record the data and your initials. Indicate the correct response.
- **Do not leave forms incomplete or unused without explanation. Do not leave items blank without explanation.** Do not skip any items. Some items may carry "unknown" or "not applicable" response choices that should be checked when necessary. Incomplete forms that do not have adequate explanation compromise the integrity of the entire study.
- **INCOMPLETE DATA:** Errors, such as incomplete and illegible forms, are problems that require time and energy to resolve. Data may not be available to complete the form for various reasons. Circle the item for which data is not available and indicate the reason near the appropriate field:
 - If an evaluation was **not done**, write "ND" and provide a reason
 - If the information is **not available**, but the evaluation was done, write "NAV". Every effort should be made to obtain the information requested.

Only in rare circumstances, as in the case of lost documentation, should NAV be recorded on the form.

- If an evaluation is **not applicable**, write “NA”.
- **INCOMPLETE FORMS:** If an entire page of the forms cannot be completed (all have no responses), and it is unlikely that it will be completed, draw a diagonal line through the form and write “NOT DONE, NOT AVAILABLE, or NOT APPLICABLE.” The header information must be completed even though no data was recorded on the form.

RETENTION OF STUDY DOCUMENTATION

NIH policy requires that studies conducted under a grant retain participant forms for 3 years (7 years if under contract). Individual IRBs may have different requirements for record retention. FDA requires that informed consent forms be retained for 2 years after a marketing application is approved for a product or, if an application is not approved, until 2 years after shipment and delivery of the product is discontinued for investigational use and the FDA is notified. Investigators should retain forms for the longest applicable period.

SOURCE DOCUMENTATION

Patient data are collected on source documents [a paper case report form (CRF)]. Source documents are any documents on which study data are recorded for the first time. The PI must retain all study documents. The following are considered subject file documents:

- Case report forms
- Data correction forms (see QRF under Administrative Forms)
- Worksheets
- Source documents
- Signed subject consent/assent forms
- Hard copies of lab reports will be placed in the CRF binder kept on site. Lab data will be sent directly electronically to the Methodology Core for updating the database.

LOCUS OF COMPUTING

- The Data Management Center (DMC) at CCHMC will design and manage the Medidata Rave database.
- The DMC at CCHMC will program the database with integrated query management. Data can be queried based on field settings, programmed logical checks, and manual checks.
- An audit trail will be maintained on all data entry. All changes made to a data point are tracked by the audit trail. The audit trail is viewable based on role permissions. Information collected in the audit trail includes: action, user name and ID, and date /time performed. A more detailed audit trail report can be generated by DMC as required.

DATA ENTRY

Only properly trained persons directly involved with the study protocol will be granted access. The DMC will invite users to the study with the appropriate role and site assignment. Users must create an iMedidata account. The iMedidata account is owned and controlled by the individual. The DMC requires role specific online Rave training before gaining access to the study database.

Double data entry will not be used for this study. Edit procedures are in place during data entry.

HEALTH INSURANCE PORTABILITY AND ACCOUNTABILITY ACT (HIPAA)

Medidata Rave complies with Health Insurance Portability and Accountability Act of 1996 (HIPPA) guidelines, by storing all data in protected areas, assigns all users roles that control data access and read/write privileges and tracks any changes. Moreover, IRB approval and patient consent is required before any data can be entered.

MEDIDATA RAVE AUDIT TRAIL:

- **Creation of data:** The data can only be entered by authorized personnel. These individuals must log onto the system with their iMedidata account username and individually selected password. Individuals should log off the system after each session to prevent unauthorized entries.
- **Modification of data:** Data modification can only be done by authorized personnel. Reasons for changes to the data will be collected. Individuals should log off after each session to prevent unauthorized entries.**Deletion** of data: Deletion of data can only be done by authorized personnel. However, subjects, forms, and log lines cannot be truly deleted. A request would need to be made to the DMC to deactivate an entire subject. The subject will be made inactive and inaccessible in EDC and will not be a part of data exports. Similarly, log lines and individual forms may also be made inactive. Users with data entry privileges are able to deactivate log lines and forms. The data will still be viewable in EDC, but will not be a part of the data export. All inactive data can be reactivated as appropriate. An **audit trail** is recorded. The audit trail includes information on: action, user name and ID, and date/time performed.

J. DATA ANALYSIS PLAN

Pharmacokinetic/dynamic analysis will occur on de-identified data by PFIZER. In brief, NONMEM modeling will be done and exposures to TOFA analyzed under consideration of patient weight and concomitant medications (steroids yes/no). All other analyses will be done by a trained biostatistician working at CCHMC .

See details in Protocol Section 8, Planned Statistical Analyses.

Categorical outcomes parameters will be summarized in frequencies/ rates and numeric outcomes will be assessed using paired t-tests. In analyses that adjust for concomitant medications, ANOVA will be done and least-square means calculated.

Frequencies of adverse events by seriousness will be summarized per MEDDRA lower level term and/or NCI Common Toxicity Criteria lower-level term.

K. REGULATORY ISSUES

ADVERSE EVENT REPORTING DEFINITIONS

Adverse Event (AE)

An AE is any untoward medical occurrence in a clinical investigation subject administered a product or medical device; the event need not necessarily have a causal relationship with the treatment or usage.

Serious Adverse Event (SAE)

An SAE is any untoward medical occurrence at any dose that:

- Results in death;
- Is life-threatening (immediate risk of death);
- Requires inpatient hospitalization or prolongation of existing hospitalization;
- Results in persistent or significant disability/incapacity (substantial disruption of the ability to conduct normal life functions);
- Results in congenital anomaly/birth defect.

Requires or Prolongs Hospitalization: Hospital admissions scheduled prior to the study, are not considered serious adverse events unless the hospitalization is prolonged due to an adverse event. Planned admissions as part of a study, hospitalizations for scheduled treatment of a pre-existing condition that has not worsened, and hospitalization for an elective procedure are not considered serious adverse events.

AE/SAE DATA COLLECTION AND REPORTING

Adverse Event Data Collection and Reporting Procedures. During a clinical trial, the reporting of adverse experience information can lead to important changes in the way a new treatment is developed, as well as provide integral safety data. All AEs will be reported on the AE pages of the CRF. All serious adverse events that occur, regardless of causality, will require immediate reporting (within 24 hours of knowledge to Pfizer. For any adverse event meeting the definition of fatal or “life threatening,” the investigator will notify Pfizer immediately. The IRB will be notified per IRB policy of SAE/AE that is both related to study drug and unexpected. All other AEs not fitting related/unexpected criteria will be reported to per IRB policy. Subjects or subjects’ partners who become pregnant during subject’s TOFA treatment will be reported on an SAE form with the addition of an *Exposure in Utero* (EIU) Supplemental Form, regardless of whether an SAE has occurred. Pregnancy SAE and EIU form will be submitted to Pfizer within 24 hours of awareness of the exposure and to the IRB per IRB policy.

See Protocol Section 7.7 Safety & Adverse Event Reporting for additional information.

WOMEN OF CHILDBEARING POTENTIAL

Patients must not be and should not become pregnant during exposure to study drug. Sexually active female participants must use an effective method of birth control during the study. The informed consent form will indicate that the investigator has reviewed information about pregnancy prevention for all women of childbearing potential. A serum or urine β -HCG will be performed at randomization. Pregnancy testing will be repeated throughout the study as deemed necessary by the treating physician.

L. RISKS & BENEFITS

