It is planned to enroll a total of 20 subjects aged 18 to 45 years with a body weight of > 40 kg with active SLE-CL that is not controlled by current standard of care medications at tolerable dosages.

Cohort 1 will undergo intense PK-evaluations during the **Intense PK Period of Part A**.

As shown in the figure above, subjects move from Part A to Part B to Part C of the study, unless they are discontinued from the study (see rescue clause, Section 6.5).

It is anticipated that almost all subjects will be treated with stable background therapy with an antimalarial (hydroxychloroquine, rarely chloroquine), up to 80% are treated with corticosteroids (CS), and about 50% of the subjects will also be treated with a non-biological DMARD (mostly methotrexate, azathioprine and mycophenolate mofetil) for prior multiorgan involvement with SLE.

Screening period

Duration up to 4 weeks; however, subjects should have the TD1 visit as soon as possible after the eligibility for the study has been confirmed.

In the event that a laboratory result does not meet inclusion/exclusion criteria for the study, the lab work may be repeated once in the four week period prior to the baseline visit to establish eligibility for the study.

If the subject fails screening for the study, they may be re-screened one time after the screen failure with permission from the sponsor. Subject will retain the same subject number as assigned at the initial study visit.

If a patient discontinues before the baseline visit, only the demographic information and inclusion/exclusion criteria with the primary reason for discontinuation should be completed on the eCRF. It is not necessary to complete all the required evaluations at the time of discontinuation unless medically indicated.

Part A (TD1 – week 8)

The primary objective of Part A is to characterize the PK of TOFA at the 5mg dose based on Cohort 1 data. Standard of care (SOC) therapies are kept stable during Part A. All background medications, including CS remain unchanged.

Cohort 1

Intense PK Period: PK sampling will only be done for subjects in Cohort 1. Starting at TD1, subject will be monitored at least weekly. PK sampling will occur pre-dose on Day 5 (approximately 11-13 hours after the second dose on Day 4) and 0.5, 1, 2, 4 and 8 hours post first dose on Day 5.

Cohort 2

Only if ≥ 1 subject of the Cohort 1 patients has shown partial response of SLE-CL to TOFA by week 4, will **Cohort 2** be enrolled.

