4.1 Primary Objective(s) & Endpoint(s)

Primary objective

Part A (Cohort 1 only):

- To evaluate the pharmacokinetic (PK) profiles of TOFA in young adults with SLE-CL who are on stable treatment for SLE

Part A (Cohort 1 and Cohort 2):

- To evaluate the safety and tolerability of TOFA in young adults with SLE-CL

Part B and C:

- To evaluate the safety and tolerability of TOFA in young adults with SLE-CL

Primary endpoints

Part A (Cohort 1 only):

- Day 5: AUC_{inf} and C_{max} of tofacitinib

Part B: At Week 24:

- Nature, severity, and frequency of adverse events
- Incidence and severity of laboratory abnormalities

[†] as early as week 8 for subjects with clinical remission of SLE -CL and off CS

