8.2 Safety Analyses

The safety population will be all subjects who received at least 1 dose of TOFA. No interim analyses are planned.

AE, SAEs and serious adverse events will be summarized using frequencies and under consideration of the number of study subjects affected. Further, in secondary analysis, we will use mixed model analysis to assess the relationship between side effects and (1) subject weight (2) background therapy with CS; (3) concurrent use of a nonbiological immunosuppressant, or (4) a history of lupus nephritis.

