1. RISKS

- **Privacy and confidentiality risks:** All study results will be kept confidential. All patient identifiers will be removed prior to data transmission to the CC at CCHMC. The study and study information will follow regulations of the Good Clinical Practice Guidelines.
- **Financial risks:** Patients will not be charged for the study procedures and study blood draws. The patient's insurance company will be charged for continuing medical care and/or hospitalization including tests and treatments of any side effects of tofacitinib. In the event that the patient insurance does not cover cost, the patient may incur additional costs because of treatment side effects.
- **Blood draws** may cause discomfort when the needle passes through the skin and may cause bruises and even infections. The study personnel will attempt to combine study blood draws with those necessary for all subjects.

The following **side-effects** are associated with Tofacitinib:

- **Very common side effects** ($\geq 10\%$): upper respiratory tract infection (nasopharyngitis, common cold).
- **Common side effects** ($\leq 10\%$): lung infection (pneumonia and bronchitis), shingles (herpes zoster), influenza (flu), sinusitis, urinary bladder infection (cystitis), sore throat (pharyngitis), viral infections affecting the gut, increased liver enzymes, muscle enzymes or cholesterol, weight gain, stomach (belly) pain (which may be from inflammation of the stomach lining), vomiting, diarrhoea, nausea, indigestion, pain in the muscles and joints, low white blood cell count, low red blood cell count (anaemia), fever, fatigue (tiredness), swelling of the feet and hands, headache, high blood pressure (hypertension), poor sleep, shortness of breath or difficulty breathing, cough, rash, itching.
- **Uncommon side effects** (1%): blood infection (sepsis), tuberculosis, kidney infection, skin infection, herpes simplex or cold sores (oral herpes), blood creatinine increased (a possible sign of decreased kidney function), dehydration, muscle strain, tendonitis, joint swelling, joint infection, ligament sprain, abnormal sensations, sinus congestion, skin redness, fatty liver, inflammation of outpouchings of the intestine (diverticulitis), tears in the stomach or intestines, viral infections, some types of skin cancers (nonmelanoma-types).
- **Rare side effects** (0.1%): tuberculosis involving the brain and spinal cord, bones and other organs, and other unusual infections.

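### Adverse events are to be tabulated by MedDRA lower-level term and/or an NCI term, with no grouping level named, so some per-term frequencies in a primary safety endpoint may be split and understated

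*Combined protocol and SAP*

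**What the plan says.** Section 4.1 lists two primary safety endpoints at Week 24: "Nature, severity, and frequency of adverse events" and "Incidence and severity of laboratory abnormalities".

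The analysis is described in two places.

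- Section 8.2 defines the population ("The safety population will be all subjects who received at least 1 dose of TOFA") and says that events will be "summarized using frequencies and under consideration of the number of study subjects affected". It names no dictionary, coding level or grouping.
- Appendix 3, section J, refers back to Section 8 for details and then gives the only rule on terms: "Frequencies of adverse events by seriousness will be summarized per MEDDRA lower level term and/or NCI Common Toxicity Criteria lower-level term".

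Three other places bear on the point. Appendix 3, section H, names the NCI Common Toxicity Criteria, Version II, for adverse event reporting, and section L repeats this. Section 7.3.8 defines a separate mild, moderate and severe scale. Section 7.3.13 asks for consistent terms between the adverse event form and the serious adverse event form, but sets no rule across subjects or across the two sites. No section names a MedDRA version or says when one dictionary is used and when the other.

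**The concern.** Lower-level terms are the finest level of MedDRA, where alternative wordings of one concept are kept apart. Preferred terms and system organ classes exist to bring them together. A frequency table built at the lowest level can therefore give one clinical event several rows, depending on how each site words it.

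The *and/or* is a second, separate weakness. It permits MedDRA, NCI terms or a mixture, and nothing fixes the choice before the data are seen.

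The trial is small and uncontrolled ("It is planned to enroll a total of 20 subjects aged 18 to 45 years"), and its size has no formal basis ("No formal sample size estimation was done but previous TOFA studies in other populations suggest that 20 subjects are sufficient"). The by-term table is where a reader learns which events occurred and how often. If one event is spread over rows of one or two subjects each, its frequency is hard to see. It is also hard to set against the frequency bands for known reactions in Appendix 3, section L.

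**Working it through.** **Plan's own figure.** There is none to reproduce: the documents give no expected adverse event rate and no formal sample size.

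**Is there a rule elsewhere that cures this?** Sections 4.1, 7.3.1 to 7.3.13 and 8.2, and Appendix 3, sections H, J, K and L, contain no preferred term, system organ class, MedDRA version or rule for choosing a dictionary. The sentence in section J stands alone.

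**Inputs for an illustration.**

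- N = 20 (planned enrolment; the safety population is all treated subjects).
- x = subjects with one given clinical event. Assumed: 4, 6 or 8.
- k = number of terms used for that event. Assumed: 1 to 4.
- Each affected subject contributes to one term only. Assumed.

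**Step 1. Largest printed row under an equal split.** Largest row = ceil(x/k)/20.

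| x of 20 | k = 1 | k = 2 | k = 3 | k = 4 |
|---|---|---|---|---|
| 4 | 20% | 10% | 10% | 5% |
| 6 | 30% | 15% | 10% | 10% |
| 8 | 40% | 20% | 15% | 10% |

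For x = 6, the exact (Clopper-Pearson) 95% intervals are 11.9% to 54.3% for 6/20, 3.2% to 37.9% for 3/20 and 1.2% to 31.7% for 2/20. The rows still add up to 6 subjects, so the count with any adverse event is unchanged.

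**Step 2. Chance that a given row shows at least 2 subjects.** With true rate p and q = p/k, this is 1 − (1−q)^20 − 20q(1−q)^19. At p = 20%:

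- k = 1, q = 0.200: 1 − 0.0115 − 0.0576 = 0.931
- k = 2, q = 0.100: 0.608
- k = 3, q = 0.067: 0.389

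**Step 3. Sensitivity to the form of the split.** At a true rate of 30%, simulation gives these means for the largest row: 30% with one term, 19.8% with two equal terms, 16.1% with three equal terms, and about 21% with three terms used in proportions 70/20/10.

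**Step 4. Against the document's own band.** Appendix 3, section L, sets very common at 10% or more, so a row of 2/20 already qualifies. With three equal terms, the chance that no row reaches 2 is the sum over j = 0 to 3 of C(3,j) × 20!/(20−j)! × (p/3)^j × (1−p)^(20−j). At p = 30% this is 0.0008 + 0.0068 + 0.0186 + 0.0159 = 0.042. In one pooled row it is 0.7^20 + 20 × 0.3 × 0.7^19 = 0.008.

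| True rate | No row reaches 10%, three equal terms | Pooled row below 10% |
|---|---|---|
| 20% | 21% | 7% |
| 30% | 4.2% | 0.8% |
| 40% | 0.5% | 0.05% |

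**The case against.** The strongest reply is that this is a descriptive table in a 20-subject single-arm study. No test, error rate, sample size or stopping rule depends on a per-term frequency. The principal investigator reviews all safety events (Appendix 3), and Section 7.3.4 already classes infections as serious or treated, whatever term is coded. Splitting happens only if the recorded wordings differ, and the data can be regrouped later. All of this stands and limits the severity. It does not remove the point, because regrouping without a stated rule is a choice made after the data are seen.

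A reader might infer that every printed frequency, or the primary safety result as a whole, is understated. The documents do not support that. Section 8.2 counts subjects affected, so the totals with any event or any serious event hold, and the laboratory endpoint is not tabulated by event term.

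A reader might also conclude that common reactions would often be hidden. Counting only rows above 10% does make the effect look large: at a 30% rate and three equal terms, the chance that no row exceeds 10% is about 28%, against 3.5% pooled. But the band in section L includes 10% itself, and on that cut-off the figures are 4.2% and 0.8%.

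Finally, section L lists "upper respiratory tract infection (nasopharyngitis, common cold" as one very common reaction. This shows that related names can be in use for one kind of event. It is a lay list with glosses, however, and does not show that the names share a preferred term. Preferred terms alone may therefore not merge them.

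**Conclusion.** The point holds as a weakness in a stated method for a primary endpoint, and it should be fixed. Appendix 3, section J, tabulates at the lowest coding level with an open choice of dictionary, and nothing elsewhere supplies a grouping. Some per-term frequencies may be understated, and the dictionary can be settled after the data are seen.

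The size depends on how many terms the sites use for one event, which the documents do not give. Under the assumed equal splits, an event in 6 of 20 subjects would print as 15% (two terms) or 10% (three terms) instead of 30%, and as 30% if one term is used. Failure of any row to reach the 10% band is uncommon at true rates of 30% or more. It becomes material near 20%, at 21% with three equal terms against 7% pooled. Sample size and error rates are not affected.

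**What to change.** Amend Section 8.2 and the sentence in Appendix 3, section J, to say the following:

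- Adverse events are coded in one named MedDRA version.
- Subjects are tabulated by system organ class and preferred term, each counted once per class and once per term.
- Pooled rows are shown for all infections and, separately, for the serious and the treated infections of Section 7.3.4. The all-infections row is needed because an infection that required no treatment, such as an ordinary cold, falls outside both of those definitions.
- Lower-level terms appear in listings only.
- NCI Common Toxicity Criteria terms are removed as a tabulation level. If those criteria are kept for grading, say so and reconcile them with the scale in Section 7.3.8.

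The cost is a few sentences and a little extra table work. No new data are needed. The change should be made before any safety table is produced.
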